COMIRB Protocol

COLORADO MULTIPLE INSTITUTIONAL REVIEW BOARD
[name] [contact] [contact]

Protocol #: 16-1785

Project Title: Evaluation of Moderate to Severe Influenza Disease in Children 6 months to 8 years in Colorado

Principal Investigator: [name]

Version Date: 7/27/16

I. Hypotheses and Specific Aims:

Children 6 months to 8 years of age with moderate to severe influenza have a higher risk of hospitalization, intensive care unit (ICU) admission, antibiotic use and complications compared with children with mild influenza illness.

Specific Aims:

Aim #1: To determine the validity of the moderate to severe endpoint for influenza as a predictor for hospitalization among children aged 6 months to 8 years evaluated at Children's Hospital Colorado (CHCO) emergency department (ED) and urgent cares (UC) during the 2016-2017 influenza season.

Aim #2: To prospectively evaluate the usefulness of the moderate to severe influenza endpoint against additional severity measures such as ICU admission, antibiotic and antiviral use, parental and child absenteeism and recurrent healthcare visits among children aged 6 months to 8 years evaluated at ED and UC centers in Colorado.

Aim # 3: To compare the healthcare costs associated with management of moderate to severe versus mild influenza disease.

Exploratory Objectives:

- 1) To compare the moderate to severe influenza definition, and other severity measures such as ICU admission, hospitalization, antibiotic, antiviral use, child and caregiver absenteeism among patients vaccinated with injectable influenza vaccine (IIV) versus unvaccinated individuals.
- 2) To evaluate severity measures such as hospitalization, ICU admission, antibiotic, antiviral use, caregiver and child absenteeism among children with influenza like illness who test negative for influenza.
- 3) To determine whether clinical measurements taken at ED/UC presentation such as systemic inflammatory response syndrome (SIRS) criteria, adjusted heart rate, oxygen saturation and temperature predict hospitalization, ICU admission and having polymerase chain reaction (PCR)-confirmed influenza. We will also consider the prediction value of peak temperature and temperature duration.

II. Background and Significance:

Influenza is an important cause of morbidity in children, annually causing 1-7 hospitalizations per 10,000 in US children under the age of 18 years (1-6). Children are

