- f. Extrapulmonary complications in patients presenting to the CHCO Main ED or North Campus UC with ILI

Definitions:

Influenza like illness (ILI): child with temperature of $\geq 37.8^{\circ}\text{C}$ and at least one of the following: cough, sore throat, runny nose or nasal congestion

Influenza: child with respiratory test that is positive for influenza by PCR

Moderate to severe influenza: child with influenza and one or more of the following criteria:

1. fever $> 39^{\circ}\text{C}$,
2. presence of otitis media defined by AAP guideline criteria,
3. lower respiratory tract infection (shortness of breath, pulmonary congestion, pneumonia, bronchiolitis, bronchitis, wheezing, croup), or
4. serious extrapulmonary manifestations (e.g., myocarditis, encephalitis, seizure)(15).

Mild influenza: child with ILI symptoms, but do not have any of the criteria for moderate to severe influenza

SIRS: Defined as the presence of two or more of the following, one of which must be abnormal temperature or leukocyte count:

1. core temperature <36 or >38.5°C
2. tachycardia (or bradycardia in infants),
3. tachypnea

Modified SIRS criteria (18): same definition as SIRS criteria excluding neutrophil criteria, i.e. the presence of two or more of the following, one of which must be abnormal temperature :

1. core temperature <36 or >38.5°C
2. tachycardia (or bradycardia in infants),
3. tachypnea

Tachycardia and tachypnea definitions by age:

Age group	Tachycardia	Bradycardia	Respiratory rate
1 month-1 year	>180	<90	>34
2-5 years	>140	NA	>22
6-12 years	>130	NA	>18

B. Description of Population to be Enrolled:

Population:

Children 6 months to 8 years of age seeking evaluation and management of ILI at the Main CHCO ED or North Campus UC will be eligible for participation in the study. The study will commence during the influenza season as determined by the department of microbiology and epidemiology at CHCO (the influenza season commences when there are 3 positive influenza PCR tests within a week). The study will continue for 5 months following the start of the influenza season.

Inclusion criteria:

- 1) Age 6 months \leq 8 years
- 2) Presentation to the CHCO Main ED or North Campus UC with signs and symptoms of ILI (temperature of $\geq 37.8^{\circ}\text{C}$ and at least one of the following: cough, sore throat, runny nose or nasal congestion)
- 3) Patients seen during the 2016-2017 influenza season

Exclusion criteria:

- 1) Respiratory symptom duration $>$ 14 days

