Aim #3/Secondary Endpoint #7 Analysis: An economic analysis will be conducted to compare the healthcare costs in the mild and moderate to severe influenza groups. We will work with the finance department at CHCO to obtain charge data for each influenza-related ED visit and hospitalization. Direct costs associated with healthcare utilization will be obtained by collecting hospital charge data and applying a cost to charge ratio to estimate costs. Mean costs and standard deviations for each group will be determined and compared using t tests for normally distributed data, and presented as median (IQR) costs with analysis conducted using non parametric tests for non-normally distributed data. Relative healthcare costs will be modeled on log-transformed data using linear regression or a generalized linear model, depending on the data distribution.

Exploratory Objective #1-2/Exploratory Endpoints #1-2: In addition to the primary and secondary outcomes outlined above, we will also assess the odds ratios and 95% CI of several exploratory dichotomous outcomes –moderate to severe influenza, hospitalization, ICU admission, antibiotics and antiviral use among patients with IIV versus unvaccinated children using log linear regression in a manner similar to the above specific aims. For continuous variables (duration of fever, number of days of absenteeism), we will use a log linear model as described for our prior secondary outcomes.
We will conduct a similar analysis as outlined above for patients with influenza like illness who test negative for influenza using the clinical severity outcome measures outlined.

Exploratory Objective #3/Exploratory Endpoint#3: We will determine the predictive value for hospitalization, ICU admission and having PCR-confirmed influenza of duration of fever, SIRS criteria, adjusted heart rate, respiratory rate and oxygen saturation using logistic regression models with two-way interactions between factors in the model when needed. We will use the Brier score to assess overall model performance and the c statistic to assess discriminative ability. In addition to logistic regression, we will explore machine learning methods for the predictive modeling of these three outcomes. The predictive value of peak temperature will also be assessed using a logistic regression model.

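### The Exploratory Objective 3 prediction models list respiratory rate with no age standardization and no age term, although the protocol's own tachypnea limits nearly halve across the enrolled ages.

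*Combined protocol and SAP*

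**What the plan says.** The Exploratory Objective #3 paragraph of Section IV.F begins: "We will determine the predictive value for hospitalization, ICU admission and having PCR-confirmed influenza of duration of fever". It continues with "SIRS criteria, adjusted heart rate, respiratory rate and oxygen saturation using logistic regression models with two-way interactions". The interactions are between factors already in the model. Machine learning methods are to be explored as well, with no inputs named, and peak temperature gets its own logistic model. On performance: "We will use the Brier score to assess overall model performance and the c statistic to assess discriminative ability".

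The objective itself (Section I, Exploratory Objectives, item 3) asks whether measurements at presentation, namely SIRS "criteria, adjusted heart rate, oxygen saturation and temperature predict hospitalization, ICU admission" and PCR-confirmed influenza. It does not name respiratory rate, and Exploratory Endpoint 3 does not list it as a measure of its own.

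Section IV.A gives a table headed "Tachycardia and tachypnea definitions by age". Its rows read "1 month-1 year >180 <90 >34", "2-5 years >140 NA >22" and "6-12 years >130 NA >18"; the last figure in each row is the respiratory-rate limit. Enrollment from 6 months to 8 years (Section IV.B) reaches all three bands.

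For Aims 1 and 2, Section IV.F names age group as a covariate chosen in advance. It extends that approach to Exploratory Objectives 1 and 2, but says nothing of the kind for Objective 3.

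**The concern.** What counts as fast breathing depends on age, and the protocol's table says so. A rate of 30 is below the limit in a 9-month-old (30/34 = 0.88 of it) and far above it in a 7-year-old (30/18 = 1.67 times it). A single respiratory-rate term without age gives both children the same contribution.

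Two opposite errors can follow. If age has little to do with the outcome, its contribution to respiratory rate is noise and a useful predictor looks weaker than it is. If younger children are admitted more often for other reasons, respiratory rate is credited with the effect of age. Either way, the term does not answer the question asked, which is what the clinical measurement itself predicts. Its comparison with heart rate, which is described as adjusted, is also uneven.

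**Working it through.** The plan gives no sample size, power or target c statistic for this objective, so there is no stated figure to reproduce.

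**1. Change in the limits (Section IV.A table).** 22/34 = 0.65 and 18/34 = 0.53. The limit falls by 1 - 0.53 = 0.47, or 47%, from the youngest band to the oldest.

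**2. Does another provision bring age in?**
- The Aim 1 and 2 covariates are extended to Exploratory Objectives 1 and 2 only.
- Interactions between listed factors cannot add an unlisted one.
- SIRS uses the age-banded limits, so it carries some age-standardized information; step 4 shows how much.

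**3. Dilution (illustrative simulation, 400,000 children).** Only the limits come from the protocol. Assumed:
- ages uniform from 0.5 to 9 years;
- limit interpolated through 34, 22 and 18 at ages 1, 3.5 and 7.5 years, and set at the mean plus 1 SD, so rate = limit - SD + SD × z, with SD of 4 or 6 breaths;
- logit(admission) = c + β × z + γ × (age - 4.5), with β = 0.6 or 1.0, γ = 0 or -0.15, and c set for 30% admitted.

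| Effect of age on admission | c, respiratory rate alone | c, rate + age + age limit | Loss within scenario |
|---|---|---|---|
| none (γ = 0) | 0.60-0.68 | 0.66-0.74 | about 0.04-0.09 |
| γ = -0.15 per year | 0.67-0.73 | 0.68-0.75 | about 0.01-0.04 |

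With γ = 0, the odds ratio per SD from rate alone is 1.23-1.66, against true values of exp(0.6) = 1.82 and exp(1.0) = 2.72.

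The comparison model is given the smooth limit that generated the data, which favors it. With the ratio of rate to the table's stepped limit (34 applied below age 2, 22 below age 6) plus age, the same simulation gives gains of about 0.03-0.07 and 0.00-0.02.

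**4. What SIRS recovers.** With γ = 0, adding the banded tachypnea flag alone to rate gives c = 0.62-0.70. Adding a binary SIRS term, which merges tachypnea with temperature and heart rate, gains only about 0.001-0.005 (fever and tachycardia assumed independent of respiratory rate).

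**5. False credit (second simulation).** Assumed: ages uniform from 0.5 to 8 or 9 years; rate log-normal around the band's limit, log-SD 0.15-0.35; outcome dependent only on being under 2 years, odds ratio 1.5-3.
- Age band explains 29-71% of the variance of respiratory rate.
- Without age, respiratory rate shows an odds ratio of 1.08-1.74 per 10 breaths and c = 0.52-0.60.
- With age band added, the odds ratio is 0.99-1.01. With rate divided by its limit, c = 0.50.

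**6. Temperature.** Item 3 of the objectives names temperature at presentation, and adds peak and duration separately. Section IV.F models duration of fever, peak temperature, SIRS (which includes a temperature criterion) and longitudinal trajectories. Presenting temperature is not a listed predictor in its own right.

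**The case against.** A reader might infer that the plan commits to raw respiratory rates. It does not say so. It never defines adjusted, even for heart rate, and the adjective could be stretched to cover the next item in the list. That reading is the less likely one: the objectives and Exploratory Endpoint 3 use adjusted heart rate as a term of its own, and no age-adjusted respiratory rate is defined anywhere.

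A reader might also infer that the planned models cannot tell the infant from the 7-year-old. That goes too far, because SIRS is in the list and uses the age bands. The objection corrects the wording more than the effect, given how little SIRS recovers in step 4.

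The strongest objection is that the aim is prediction. A c statistic or Brier score is correct for the model fitted even if a predictor partly carries age, so the reported figures would not be wrong. This stands. What remains is that the stated question concerns the predictive value of the measurements, and a term mixed with age does not isolate that.

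The size is also open to challenge, and rightly. The larger losses need age to have no effect on admission, whereas the plan itself treats age group as something that could affect hospitalization. The simulations cover respiratory rate alone (with SIRS added in step 4), not the full set of predictors, and step 3 covers admission only, not ICU admission or PCR-confirmed influenza.

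Finally, the temperature gap does not mean temperature is neglected; three other analyses use it, and so does SIRS.

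**Conclusion.** The point holds as a modest improvement to an exploratory analysis. The listed models contain respiratory rate with no age standardization and no age term, while the protocol's own limits show that the meaning of a given rate changes by nearly half across the enrolled ages. Fitted as listed, the term is diluted by age or absorbs its effect.

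For respiratory rate alone, the loss in c statistic is about 0.01-0.04 if age affects admission, the case the plan's own covariate list makes more plausible, and 0.04-0.09 if it does not. Both ranges rest on the assumed age distribution, spread, admission rate and slopes. The loss in the full multi-predictor model has not been estimated. No primary or secondary result depends on this. The missing presenting-temperature term is a separate, smaller mismatch between objective and analysis.

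**What to change.** In the Exploratory Objective #3 paragraph of Section IV.F:

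- enter respiratory rate relative to age, for example as a ratio to or excess over the protocol's age limit (a limit smoothed over age loses less than the stepped one in the check above);
- include age in every Objective 3 regression and machine learning model;
- define adjusted heart rate, and say that it means age-adjusted if that is the intention;
- add presenting temperature to the listed predictors, to match the objective.

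The cost is a sentence or two of text, one or two extra model terms for age and respiratory rate, and one for temperature. Age, respiratory rate and temperature are already needed for eligibility or for SIRS, so no new data are required.

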The purpose of the proposed study is to validate that the definition of moderate to severe influenza in children predicts greater risk of healthcare endpoints such as hospitalization, increased length of stay, use of antimicrobials (including antivirals), absenteeism, increased duration of illness, and increased healthcare costs.

Understanding and validating the relationship between moderate to severe influenza and these clinically relevant endpoints is critical to establishing relevant surrogate markers of clinical and public health outcomes. If shown to be clinically relevant, this definition of moderate to severe influenza can be an important endpoint for assessing influenza vaccine effectiveness.

III. Preliminary Studies/Progress Report:

CHCO provides an ideal site for the study of influenza in children. CHCO is a large tertiary institution with a large catchment area of Denver Metro, Aurora and surrounding states. It serves 67% of children in the state of Colorado. From December 1, 2010 to April 30, 2014, there were 409 patients admitted to CHCO with PCR-confirmed influenza; 62% of these were defined as high-risk (16), and 38% were vaccinated against influenza during the same season. Accurate immunization data was available for 83% of patients via the Colorado Immunization Information System (CIIS). Clinical presentation and

hospital-based outcomes such as length of hospitalization among children admitted with influenza are shown in Table 1.

Table 1. Children Admitted To CHCO with Influenza, 2010-2014

Children admitted to CHCO with influenza N = 395	< 3 years N = 156	>3 years N = 239
Otitis media	10 (6)	6 (3)
Pneumonia	7 (5)	22 (9)
Hypoxia	19 (12)	141 (59)
Fever	133 (85)	207 (87)
Median duration of fever, days (range)	2 (1-17)	4 (1-64)
Tachypnea	64 (41)	91 (38)
Antibiotics	88 (56)	157 (66)
Median duration of antibiotics, days (range)	7 (0-23)	8 (0-77)
Pediatric Intensive Care Unit (PICU)	55 (35)	81 (34)
PICU length of stay, days	2 (1-100)	3(1-83)
Death	1 (1)	2 (1)
Median duration of hospitalization, days (range)	3 (1-100)	3 (1-128)
Vaccinated during current season against influenza	39 (25)	87 (36)

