Preliminary data from the 2013-2014 and 2014-2015 influenza seasons demonstrated that among 11,997 patients who presented to CHCO ED, UC or outpatient clinics for an acute respiratory illness, 1398 (12%) underwent viral testing (either respiratory pathogen panel multiplex PCR or influenza PCR). 1375 patients were admitted for a respiratory illness, and of these, 994 (72%) underwent viral testing. Additional data regarding ED visits during these time periods are shown in Table 2.

Table 2. Children Presenting to CHCO ED or UC with Acute Respiratory Illness, 2013-2014 and 2014-2015

CHCO data:	2013-2014	2014-2015	Total
ED/UC/Clinic visits due to an acute respiratory illness	5900	6097	11997
ED visits due to an acute respiratory illness, limited to patients < 8 yrs	4510	4595	9105
ED visits limited to CHCO, Uptown Urgent Care, South Urgent Care with an acute respiratory illness, limited to patients < 8 yrs	2703	2809	5512
ED visits with above restrictions further limited to Jan to March	1290	1745	3035
Limit visits to < 8 yrs Jan to March, no repeat visits	1244	1688	2932
Admission for acute respiratory illness,	454	486	940

Jan -Mar

IV. Research Methods

The study comprises a prospective analysis of children presenting to CHCO ED, and North Campus UC with an influenza-like illness (ILI) during the 2016-2017 influenza season. Once enrolled in the study, we will collect respiratory samples (nasopharyngeal (NP) specimens), socio demographic, and clinical data including variables of interest outlined above, and follow the clinical outcome of these children for 14 days after their initial presentation. A complete list of the variables being collected can be found in Appendix A.

A. Outcome Measure(s):

Primary outcome measure /Endpoints:

- 1) Hospitalization in patients presenting to the CHCO Main ED or North Campus UC with influenza

Secondary outcome measures/Endpoints:

- 1) ICU admission in patients presenting to the CHCO Main ED or North Campus UC with influenza
- 2) Antiviral use in patients presenting to the CHCO Main ED or North Campus UC with influenza
- 3) Antibiotic use in patients presenting to the CHCO Main ED or North Campus UC with influenza
- 4) Number of visits to the ED or healthcare provider in patients presenting to the CHCO Main ED or North Campus UC with influenza
- 5) Number of days of absenteeism from school or daycare in patients presenting to the CHCO Main ED or North Campus UC with influenza

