To compare temperature trajectories between hospitalized and non-hospitalized, we will use a linear mixed model. This will allow us to use all of the longitudinal temperature measurements to measure the mean temperature trajectory of patients in one group (e.g. hospitalized patients) compared to the other (e.g. non-hospitalized patients). We will accomplish this by including an interaction term between time and hospitalization status, which will give us hospitalization status-specific trajectories. We will do this for each

dichotomous outcome: hospitalization, ICU status, influenza diagnosis. This method is preferred over subgroup analysis because it will optimize statistical power.

[figure not shown]
Two sensitivity analyses will be conducted. Firstly, analyses will be restricted to patients presenting to the main CHCO ED. Secondly, to further evaluate whether temperature $> 39^{\circ}\text{C}$ is a predictor of healthcare utilization or poorer outcomes, an analysis of each of the secondary outcome measures will be conducted. Firstly, we will compare all moderate to severe versus mild influenza cases. If these reach statistical significance with an odds ratio > 1 , we will then repeat the analysis with a definition of moderate to severe influenza as solely temperature $> 39^{\circ}\text{C}$.

Power and sample size calculations:

Using historical data from our institution, a sample size of 408 patients (of which we assume 30% have mild flu and 70% have moderate/severe flu) will achieve 80% power at a 0.05 significance level to detect an odds ratio of approximately 2 for hospitalization among the moderate/severe compared to the mild cases, accounting for the inclusion of correlated covariables in our multivariable model. Assuming that 25% of patients tested will be influenza positive (19) during the influenza season; we will need to test approximately 1632 subjects (Figure 1). A sample size of 151 patients with the same assumptions, power and significance level will detect an odds ratio of 3 for hospitalization among the moderate/severe compared with mild cases, so 604 subjects will need to be tested.

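### The fever-only sensitivity analysis does not say who is in either group; read literally, it compares above with not above 39 °C and cannot show whether fever as the only criterion marks illness worse than mild

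*Combined protocol and SAP*

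**What the plan says.** Section IV.A sets the two severity groups. The first is "Moderate to severe influenza: child with influenza and one or more of the following criteria": fever above 39 °C, otitis media, lower respiratory infection, or serious extrapulmonary manifestations. The second is its complement: "Mild influenza: child with ILI symptoms, but do not have any of the criteria for moderate to severe influenza".

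Section IV.F plans two sensitivity analyses. The second asks whether temperature above 39 °C "is a predictor of healthcare utilization or poorer outcomes", and for this "an analysis of each of the secondary outcome measures will be conducted". It has two steps. The first is the composite comparison: "Firstly, we will compare all moderate to severe versus mild influenza cases". If that is significant with an odds ratio above 1, the second step is to "repeat the analysis with a definition of moderate to severe influenza as solely temperature" above 39 °C. The text does not restate the comparator, and does not say where to put children who qualify only on a non-fever criterion or children who have fever plus another criterion.

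The wider aim, in section II, is to "validate that the definition of moderate to severe influenza in children predicts greater risk of healthcare endpoints such as hospitalization".

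**The concern.** Mild is defined by what moderate to severe is not. If the second is narrowed to one criterion and nothing else is said, the first widens. A child with pneumonia, otitis or a seizure and a temperature of 39 °C or less then counts as mild. At the same time, the fever group may hold children whose risk comes from pneumonia rather than from fever.

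The study sets out to validate a composite, and this is the planned analysis of its 39 °C criterion. A reader will want to know whether a child who qualifies on fever alone is sicker than a mild case. An odds ratio from two mixed groups does not answer that, and could be taken as evidence for or against the fever criterion. Because several readings are open, the choice could also be made after the data are seen.

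A smaller point concerns the entry condition. An odds ratio above 1 cannot be applied literally to secondary endpoints 4–7: visits and the two absenteeism outcomes are to be reported as geometric mean ratios, and costs are modelled on a log or generalized linear scale.

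**Working it through.** **Inputs from the plan.** Section IV.F gives 408 influenza-positive children, 30% mild and 70% moderate to severe: 408 × 0.30 = 122 and 408 × 0.70 = 286. It gives no figure for the fever analysis, so there is none to reproduce.

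**Assumed inputs.** f = share of moderate to severe cases without fever above 39 °C (10%, 20%, 50%); v = share of febrile children who also meet another criterion (0%, 30%, 50%); the outcome risk in mild cases; and the odds ratios (OR) of the subgroups against original mild. The documents give none of these. Table 1 covers admitted children only and has no 39 °C cut.

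**Step 1: children who move under the literal reading.** Number = 286 × f; share of the new reference group = 0.70f / (0.30 + 0.70f).

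| f | moved | share of reference |
|---|---|---|
| 10% | 29 | 19% |
| 20% | 57 | 32% |
| 50% | 143 | 54% |

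**Step 2: formulas.**
- Reference risk = (0.30 × p_mild + 0.70f × p_other) / (0.30 + 0.70f)
- Febrile risk = (1 − v) × p_feveronly + v × p_other
- Fever OR = odds(febrile) / odds(reference)

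**Step 3: equal risk in all moderate to severe cases, OR 2.0.** With p_mild = 0.10, p_feveronly = p_other = 0.182. At f = 20% the reference risk is (0.030 + 0.14 × 0.182) / 0.44 = 0.126, and the fever OR is 0.2222 / 0.1442 = 1.54. Over mild risks of 2–40% the OR is 1.69–1.75 (f = 10%), 1.52–1.60 (20%) or 1.30–1.38 (50%). Overlap has no influence here.

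**Step 4: unequal risk.** p_mild = 0.10 and any other criterion OR 4 (risk 0.308), with or without fever.

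| Fever-only OR (true) | v | f = 10% | f = 20% | f = 50% |
|---|---|---|---|---|
| 1.5 | 0% | 1.03 | 0.84 | 0.62 |
| 1.5 | 30% | 1.47 | 1.20 | 0.89 |
| 1.5 | 50% | 1.80 | 1.46 | 1.08 |
| 1.0 | 30% | 1.20 | 0.97 | 0.72 |
| 1.0 | 50% | 1.58 | 1.29 | 0.95 |

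The literal contrast can lie below or above the fever-only OR. It can exceed 1 when fever alone adds nothing.

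**Step 5: same data, different readings.** Take f = 20%, v = 30%, fever-only OR 1.5, other criteria OR 4, p_mild = 0.10. The febrile risk is 0.7 × 0.143 + 0.3 × 0.308 = 0.192 (odds 0.238); the enlarged reference risk is (0.030 + 0.14 × 0.308) / 0.44 = 0.166 (odds 0.199).
- Literal (all febrile versus enlarged mild): 0.238 / 0.199 = 1.20.
- Original mild kept, all febrile children in the fever group: 0.238 / 0.111 = 2.14.
- Original mild kept, fever as the only criterion: 1.50.

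**Step 6: precision of the fever-only contrast.** Wald 95% intervals, unadjusted, true OR 2.0, 122 mild children. Fever-only children: 286 × (1 − f)(1 − v) = 286 × 0.25 ≈ 72 at f = v = 50%; as a generous upper value, 286 × 0.70 ≈ 200.

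| Mild risk | 72 children | 200 children | composite (286) |
|---|---|---|---|
| 10% | 0.86–4.64 | 1.00–4.00 | 1.03–3.88 |
| 20% | 1.03–3.87 | 1.17–3.41 | 1.20–3.32 |

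**The case against.** The strongest reply is that the plan asks whether temperature above 39 °C is a predictor, and above versus not above 39 °C answers that. This stands: the contrast is legitimate, and whether fever alone is worse than mild is a further question. It is still the question that bears on validating a composite, and the plan does not say which of the two it means.

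Second, the text need not be read literally. Mild may keep its original meaning, with the remaining children in neither group, and 'solely' may mean fever as the only criterion. If both hold, the planned contrast is already fever-only versus original mild. This also stands, so a reader should not infer that children with pneumonia or seizure will certainly be counted as mild. The defect is that the text does not choose, and Step 5 shows that the choice changes the result.

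Third, every bias figure is assumed. That is correct. A reader might infer a bias towards no effect; the documents do not support this, because overlap works the other way, and if all groups shared the mild-group risk nothing would change.

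Fourth, the secondary points are small. The intent of the odds-ratio condition can be guessed. The primary endpoint, "Hospitalization in patients presenting to the CHCO Main ED or North Campus UC with influenza", is absent from this analysis by explicit scope, which is a choice and not a contradiction. Peak temperature and temperature trajectories are related to hospitalization elsewhere in section IV.F, though without the 39 °C cut.

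**Conclusion.** The concern holds in limited form. The fever analysis defines neither of its groups, and under the literal reading it cannot show whether fever as the only criterion marks illness worse than mild. Size and direction are unknown from the documents. With equal risk in all moderate to severe cases, a true odds ratio of 2.0 becomes about 1.75 to 1.30 when 10–50% of them lack fever above 39 °C; with unequal risks and overlap it can move either way. All of this rests on assumed risks, shares and overlaps, apart from the 408 children and the 30/70 split.

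It would go too far to call the planned contrast invalid or to carry the point over to the main result. This is a conditional sensitivity analysis of secondary outcomes, and the primary hospitalization analysis is unaffected. The change should be made before analysis, but the study does not stand or fall on it.

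**What to change.** In section IV.F, name both groups. Keep the original mild group (no criterion met) as reference and fit a three-level exposure:
1. mild;
2. fever above 39 °C as the only criterion;
3. any otitis, lower respiratory or extrapulmonary criterion, with or without fever.

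Fit it for each secondary outcome, and optionally for hospitalization, with that outcome's own measure: odds ratio for endpoints 1–3 (and hospitalization), geometric mean ratio for 4–6, cost ratio for 7. Report above versus not above 39 °C among all influenza-positive children as a separately named contrast. If the entry condition is kept, word it as significant with an effect ratio above 1, so that it fits endpoints 4–7. Label both contrasts supportive.

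The cost is some wording, a few more models and comparisons on data already collected, and the wider intervals of Step 6. At a 10% mild risk the fever-only contrast may be inconclusive even at a true odds ratio of 2.0; at 20% the intervals exclude 1. Rare outcomes such as ICU admission may have to be descriptive only.
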